2.2 Secondary Objectives

The secondary objectives of this study are:

- To measure and compare patient reported outcomes (e.g., VAS, Patient Satisfaction and ODI) at baseline and final follow-up
- To measure and compare clinical and radiologic outcomes at baseline and final follow-up
- To measure and compare the clinical, radiologic, and patient reported outcomes at interim follow-up visits
- To assess the impact of demographics and risk factors on clinical, radiologic, and patient reported outcomes

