4.2 Data Collection Summary

Subjects will have undergone a decompression surgery with the coflex® Interlaminar Technology, 1 or 2 level decompression with or without fusion according to the physician's standard procedures. Table 1 describes the anticipated time points which will be collected as part of the retrospective data review. Please see Section 4.4, Data Collection Procedures for additional details regarding the data points intended to be captured at the designated time points.

	Baseline	Surgical Treatment	Post-Operative Hospital Stay	Follow-Up Visit(s)
Demographics & Risk Factors	X			
Prior Surgery Detail (If available)	X			
Diagnosis	X			
Operative Summary		X		
Procedure Payer Information		X		
Secondary Treatments			X	X
Complications		X	X	X
Work Status / ADL (If available)	X		X	X
Patient Questionnaires (If available)	X	X	X	X
Diagnostic Imaging History	X	X	X	X

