4.4.1 Baseline Visit

- Diagnosis
 - Presenting symptoms
 - Documented failed conservative treatment
 - Patient reported outcome questionnaires, if available
 - Prior treatment details
- Pre-Operative Demographics
 - Date of visit
 - Age
 - Gender
 - Race
 - Ethnicity
 - Work Status / ADL
 - Height (in)
 - Weight (lbs)
 - BMI

- Risk Factors
 - Tobacco Use
 - Alcohol Use
 - Comorbidities
 - Diabetes
 - Bone Density
 - Medications
- Diagnostic Imaging
 - MRI and CT of affected lumbar levels
 - Radiographs

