4.4.4 Follow-Up Visits

The following longitudinal data will be collected for all follow-up clinic visits through final follow-up:

- Work status / ADL
- Compliance with postoperative protocol/restrictions (if applicable)
- VAS (as available)
- ODI (as available)
- Patient satisfaction (as available)
- Complications
- Secondary treatments
- Narcotics use
- Diagnostic Imaging
- Incidence of Epidural Steroid Injections (ESI)

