5.0 Statistical Analysis

5.1 General Information

All continuous outcome measurements at follow-up time points will be compared to baseline values using a t-test for superiority. Categorical outcome measurements will be compared using a Fisher's exact test for superiority. Statistical significance for these analyses will be demonstrated with a p-value less than 0.05.

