5.3 Secondary Endpoints

The clinical outcomes will be summarized; however, since the collection of these measures is not standard of care, this data will only be collected as available. In addition, data will be used to analyze the association between coflex® Interlaminar Technology use and outcomes with age, ethnicity, race, workers' compensation, smoking status, and gender. New and/or worsening complications will be summarized.

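### Patient reported outcomes are compared with baseline at an undefined final follow-up, on whatever scores exist, so the result is hard to interpret and may be biased

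*Combined protocol and SAP*

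**What the plan says.** **Time point.** Section 2.2 (repeated in the Protocol Summary) lists as secondary objectives "To measure and compare patient reported outcomes (e.g., VAS, Patient Satisfaction and ODI) at baseline and final follow-up" and "To measure and compare the clinical, radiologic, and patient reported outcomes at interim follow-up visits". Section 4.2 says that "Table 1 describes the anticipated time points which will be collected as part of the retrospective data review", but the table has a single follow-up column with no months. Section 4.4.4 states that "longitudinal data will be collected for all follow-up clinic visits through final follow-up". Neither the final nor the interim visits are given a time.

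**Length of follow-up.** Section 2.1 makes the duration of follow-up a primary objective, and Section 5.2 analyses it as part of the primary endpoint.

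**Availability.** Section 4.4.1 asks at baseline for "Patient reported outcome questionnaires, if available". Section 4.4.4 marks VAS, ODI and satisfaction in the same way at follow-up, and the Section 4.2 table does so at every stage. Section 5.3 gives the reason: "since the collection of these measures is not standard of care, this data will only be collected as available".

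**Analysis.** Section 5.1: "All continuous outcome measurements at follow-up time points will be compared to baseline values using a t-test for superiority", with p below 0.05 as the threshold. It does not say whether the test is paired. It gives no term for time since surgery, no method for missing scores and no comparison of patients with and without scores.

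**Rank of the outcome.** Section 4.1 places patient reported outcomes under the primary objective, while Section 2.2 lists them as secondary.

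**The concern.** There are two separate problems.

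The first is what is being estimated. With no window, a patient last seen a few weeks after surgery and one last seen years later enter the same mean. If scores still change over that span, the mean reflects the visit pattern of the contributing practices as well as the effect of surgery. This is not bias in the strict sense: the figure is a correct mean at last visit. But it answers no stated clinical question, and it would differ in another set of sites with the same recovery.

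The second is who is scored. Because the questionnaires are not routine care, patients with scores may differ from those without. If having a score is related to how the patient is doing, the mean is biased for the treated population.

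The Protocol Summary and Section 1.0 say that the data are meant to support publications and marketing. The size of the improvement is what readers would take from them, and it is the size that is exposed.

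**Working it through.** **Plan's own figure.** The only relevant number is about 5000 patients from 50 sites (Protocol Summary). It has no effect size, SD or power behind it, so there is nothing to reproduce, and it is not in dispute. Apart from that number, every input below is assumed, including a 0–100 scale; positive means improvement. The results show what can happen, not what will.

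**1. Timing.** Let *s* be the share of patients last scored early (say at 3 months), with the rest last scored at 12 months or later.

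Mean at last visit = *s* × early + (1 − *s*) × late

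| Early / late mean change | *s* = 0.2 | *s* = 0.5 | *s* = 0.8 |
|---|---|---|---|
| 25 / 35 (still improving) | 33 | 30 | 27 |
| 35 / 25 (benefit fades) | 27 | 30 | 33 |

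For example, 0.2 × 25 + 0.8 × 35 = 5 + 28 = 33. The spread is 33 − 27 = 6 points with identical recovery in every patient. If early equals late, the formula returns that common value for every *s*, so the effect of timing is zero.

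**2. What the p-value can show.** For a mean change, the 95% half-width is t × SD/√n.

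- n = 500 (10% of 5000), SD 30: 2.6 points (2.2 for SD 25, 3.1 for SD 35).
- n = 2500, SD 30: 1.2 points.
- At the lowest mean in the table, t = 27/(30/√500) = 20.1.

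On these inputs, any mean change above 2.6 points is already significant with 500 scored patients. The test is passed whether the mean is 27 or 33, so it neither reveals the problem nor is overturned by it. A larger sample does not remove the problem.

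**3. Availability.** Suppose 70% of patients improve by 40 points and 30% by 10. The true mean is 0.7 × 40 + 0.3 × 10 = 31.0. With availability *a*₁ in the first group and *a*₂ in the second:

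Observed mean = (0.7*a*₁ × 40 + 0.3*a*₂ × 10) / (0.7*a*₁ + 0.3*a*₂)

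- *a*₁ = 0.6, *a*₂ = 0.4: 18.0/0.54 = 33.3
- *a*₁ = 0.5, *a*₂ = 0.5: 15.5/0.50 = 31.0 (no bias)
- *a*₁ = 0.4, *a*₂ = 0.6: 13.0/0.46 = 28.3

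**4. Paired or unpaired.** Section 5.1 allows either reading.

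- *Paired:* only patients with both scores count. If each score exists for 30%, 50% or 70% of patients, independently, then 0.3² = 9%, 0.5² = 25% or 0.7² = 49% have both (450, 1250 or 2450 of 5000). Without independence, 50% and 50% allow anything from 0% to 50%.
- *Unpaired:* all scores are used, but the baseline and follow-up means come from partly different patients, so their difference can reflect a change in who is measured.

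As-available collection matters under both.

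**The case against.** **It is disclosed.** Section 5.3 says openly that these measures are collected as available and will be summarised. That is fair, but it tells the reader that scores will be missing, not how the analysis allows for it. Section 5.1 still plans superiority tests.

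**Interim visits are compared too.** This would help if those visits had times. They have none.

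**The numbers are invented.** This stands. The 10-point gap between early and late, the 20% to 80% contrast and the sample sizes are all chosen. They support no statement about the likely size in this study.

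**The consequence is limited.** This largely stands. A reader might infer that the significance tests against baseline are unsafe; the working gives no ground for that. A reader might also infer that the comparison of coflex with decompression or fusion is biased. The plan states no between-group test of these scores, and such a reading would be affected only if timing or availability differed between groups, on which the documents are silent. Nor can it be said that the plan's confidence interval would be too narrow, because the plan promises none.

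**It is only a secondary outcome.** Section 2.2 says so, but Section 4.1 says otherwise, so this defence is not available until the two are reconciled.

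**Conclusion.** The point holds, and the sponsor should act on it. The analysis time is undefined, and follow-up length varies by the plan's own account. The result is therefore an average over uncontrolled recovery times, hard to interpret unless recovery is flat. Reading it as each patient's last visit is an inference, but it is the only workable one without a schedule.

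It would go too far to call the timing part bias, or to say that bias has been shown. Bias enters only through availability, and only if availability is related to outcome. If recovery is flat and availability is unrelated to outcome, neither problem changes the estimate of mean change among patients with both scores.

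Size and direction cannot be obtained from the documents. The 6-point spread and the deviations of +2.3 (33.3 − 31.0) and −2.7 (28.3 − 31.0) points are illustrations. If Section 4.1 governs, the weakness reaches a primary outcome.

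**What to change.** 1. **Main analysis time.** Name one window from index surgery, chosen by the sponsor before results are seen, and state which score counts if several fall in it. Check it against surgery dates: if the April 2017 end date is the data cut-off, patients operated on after April 2016 cannot supply a 12-month score, nor those operated on after April 2015 a 24-month score. Define interim windows in the same way, and keep the last-visit result as descriptive.
2. **Model.** For the scores analysed as continuous, replace the t-test with a repeated-measures model on all available scores, with time since surgery and site. Enter baseline as the first repeated measurement, not also as a covariate, so that patients without a baseline score are kept.
3. **Availability.** Report by treatment group and window how many patients have scores, and the baseline features of those with and without them.
4. **Sensitivity.** Add a simple analysis for scores missing not at random, such as shifting unobserved scores by up to 10 points in either direction. With 30%, 50% or 70% missing, a 10-point shift moves the overall mean by 3.0, 5.0 or 7.0 points (share missing × 10).
5. **Rank.** Reconcile Sections 2.2 and 4.1.

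**Cost.** If visit dates are on the CRF, this is SAP wording and analysis only. Section 4.4.2 collects the date of surgery, and a duration endpoint implies a last-visit date, but Section 4.4.4 lists no visit date. This must be confirmed. If dates are absent, one date per visit has to be abstracted; across about 5000 charts at 50 sites, between a November 2016 protocol and an April 2017 end date, that is not trivial.

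**Downside.** Fewer patients contribute at later windows, and those still attending may be a selected group. The model corrects for this only as far as earlier scores and the other model terms explain attendance; items 3 and 4 are there to expose the rest.

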3.0 Eligibility Criteria

3.1 Inclusion criteria

Patient considered for enrollment in this study must meet all of the following inclusion criteria:

- Patients must meet the criteria specified in the device labeling including radiographic confirmation of at least moderate lumbar stenosis, which narrows the central spinal canal at one or two contiguous levels from L1-L5 that require surgical decompression.

3.2 Exclusion criteria

There are no exclusion criteria for this study.

4.0 Study Design

This is a retrospective, multi-center, post-market study collecting clinical, radiographic, and patient reported outcomes for subjects who have been treated 1 or 2 levels with the coflex® Interlaminar Technology or decompression with or without fusion.

4.1 Endpoints

Patient reported outcomes will be assessed as part of the primary objective.

Clinical and radiologic outcomes, demographics and risk factors will be assessed as part of the secondary objectives. These include, but are not limited to:

- Age
- Gender
- Ethnicity
- Height and Weight
- BMI
- Narcotics use
- Comorbidities
- Bone Density
- Presenting Symptoms
- Radiologic Data (Anterior/Posterior and Flexion/Extension films, as well as, MRI and/or CT Scan used to confirm diagnosis of spinal stenosis)
- Operative Data
- Intra-Operative Complications
- Return to Work
- Changes in Activities of Daily Living (ADL)
- Patient Satisfaction
- Repeat Surgery Details

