Study Design	Retrospective, multi-center, post-market clinical study
Devices	coflex® Interlaminar Technology
Data Collection	Clinical, radiologic and patient reported outcomes data will be collected for approximately 5000 patients from 50 sites
Study Duration	Up to 6 months for data collection Start Date: June 2013 End Date: April 2017
Study Objectives	
Primary Objective:
 
• To assess the operative details and safety outcomes associated with the use of the coflex device• To assess post-operative adverse events• To assess post-operative follow-up duration 
Secondary Objectives:
 
• To measure and compare patient reported outcomes (e.g., VAS, Patient Satisfaction and ODI) at baseline and final follow-up• To measure and compare clinical and radiologic outcomes at baseline and final follow-up• To measure and compare the clinical, radiologic, and patient reported outcomes at interim follow-up visits• To assess the impact of demographics and risk factors on clinical, radiologic, and patient reported outcomes•
Inclusion Criteria	Patients must meet the criteria specified in the device labeling including radiographic confirmation of at least moderate lumbar stenosis, which narrows the central spinal canal at one or two contiguous levels from L1-L5 that require surgical decompression.
Exclusion Criteria	There are no exclusion criteria's for this study.

Risk/Benefit Assessment

The study is a retrospective analysis of medical records that poses no risk to the patients and minimal risk to loss of patient privacy. All results will be de-identified in the process of data review. There are no benefits to the subject as this data is being collected to obtain additional clinical evidence to support publications and marketing.

Study Abbreviations

Abbreviation	Definition
BMI	Body Mass Index
FDA	Food and Drug Administration
GCP	Good Clinical Practice
HIPAA	Health Insurance Portability and Accountability Act of 1996
ICH	International Committee on Harmonization
IRB	Institutional Review Board
MRI	Magnetic Resonance Imaging
CT	Computed Tomography
DEXA	Dual Energy X-ray Absorptiometry

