2.0 Study Purpose

2.1 Primary Objective

- To assess the operative details and safety outcomes associated with the use of the coflex device
- To assess post-operative adverse events
- To assess post-operative follow-up duration

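### The protocol is inconsistent about which outcomes are primary, and neither endpoint in section 5.2 has a complete analysis

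*Combined protocol and SAP*

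**What the plan says.** The Protocol Summary and section 2.1 give the same three primary objectives: "To assess the operative details and safety outcomes associated with the use of the coflex device", "To assess post-operative adverse events" and "To assess post-operative follow-up duration". The Summary and section 2.2 then list as secondary "To measure and compare patient reported outcomes (e.g., VAS, Patient Satisfaction and ODI) at baseline and final follow-up".

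Section 4.1 opens differently: "Patient reported outcomes will be assessed as part of the primary objective". It continues: "Clinical and radiologic outcomes, demographics and risk factors will be assessed as part of the secondary objectives". An open-ended list follows, containing among others operative data, "Intra-Operative Complications", patient satisfaction and "Repeat Surgery Details".

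Section 5.2, on the primary endpoint, names length of follow-up care and the incidence of secondary surgical interventions, and presents them as measures of effectiveness. It says they will be analysed but not how. Section 5.3, on secondary endpoints, summarises new or worsening complications.

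The only tests are in section 5.1: a t-test of continuous follow-up measurements against baseline, and Fisher's exact test for categorical outcomes with no comparator named. Both are described as superiority tests, with significance at p below 0.05.

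**The concern.** A reader cannot tell from the text which result is the study's primary claim. Patient-reported outcomes, adverse events or secondary surgery could each be presented as primary with support from some section, and no section takes precedence over the others. This matters because section 5.1 speaks of superiority and statistical significance, and the Introduction says the data are meant to support publications and marketing. The data already sit in medical charts and are analysed by the sponsor's representatives, so the protocol text is the main safeguard against choosing the primary result after seeing it.

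The second part concerns secondary surgery, the clinical event named in section 5.2. If the groups are compared on crude incidence and one was followed longer, a difference can appear with no true difference in reoperation.

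**Working it through.** **Step 1: designations side by side.** The plan states no figure to reproduce here, so the check is textual.

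| Outcome | Called primary in | Called secondary in | Strength of conflict |
|---|---|---|---|
| Patient-reported outcomes | 4.1 opening sentence | Summary, 2.2 (absent from 5.2) | Firm |
| Adverse events / complications | Summary, 2.1 | 5.3; intra-operative complications also in 4.1 list | Firm |
| Operative details | Summary, 2.1 | 4.1 list only | Weak |
| Secondary surgery | 5.2 | 4.1 list only | Weak |
| Length of follow-up | Summary, 2.1, 5.2 | Nowhere | None |

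The second row depends on adverse events and complications being the same data. The table in section 4.2 and the items in sections 4.4.2 to 4.4.4 collect complications and have no separate adverse-event item, so one set of data serves both levels.

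**Step 2: is there a method for each endpoint in section 5.2?** Length of follow-up: none is stated. Secondary surgery: Fisher's exact test in section 5.1 is the only candidate. It can be read in two ways.

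- *Against baseline.* Surgery after the index operation is zero at baseline by construction. With 5000 patients, 5 events against 0 gives p = 0.062, and 6 against 0 gives p = 0.031. Such a result means nothing, and the test also assumes independent samples.
- *Between groups.* The reference group, the time point and the handling of unequal follow-up are all missing. Section 4.4.4 collects every visit up to final follow-up, with no fixed horizon.

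**Step 3: what unequal follow-up can do to a crude comparison.** The documents give no reoperation rate, group sizes or follow-up lengths, so all inputs here are assumptions. Both groups have the same hazard h per year, and all patients in a group are followed for t years. The probability of at least one event is p = 1 − exp(−h × t). For h = 0.04:

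- t = 1: p = 1 − exp(−0.04) = 0.0392
- t = 1.5: p = 1 − exp(−0.06) = 0.0582
- t = 2: p = 1 − exp(−0.08) = 0.0769

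Event counts were simulated from these probabilities (1000 runs per scenario) and tested with a two-sided Fisher test at 0.05. Ranges cover h = 0.02 to 0.06.

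| Patients per group | 1 vs 1 year | 1 vs 1.5 years | 1 vs 2 years |
|---|---|---|---|
| 2500 and 2500 | 4% to 5% | 57% to 97% | 98% to 100% |
| 4000 and 1000 | 4% to 5% | 45% to 87% | 90% to 100% |
| 500 and 500 | 3% to 4% | 15% to 33% | 36% to 88% |

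With equal follow-up the test behaves as it should. With unequal follow-up it rejects too often, and the group followed longer looks worse although the hazards are equal.

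**The case against.** The strongest reply is that the section 4.1 sentence is one stray line against a Summary, section 2.2 and section 5.2 that do not make patient-reported outcomes primary, and that a wording correction settles it. It is indeed cheap to correct. But it stands in the section headed Endpoints, and it does not explain why complications are secondary in section 5.3 when adverse events are primary in section 2.1.

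Several stronger readings are tempting, and the documents do not support them.

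- A reader might infer from the table that four of the five outcomes conflict. Two of those four rest only on the section 4.1 list, which mixes age, gender and BMI with outcomes and is expressly not exhaustive. It can equally be read as an inventory of data. The defensible count is two.
- A reader might infer that sections 2.1 and 5.2 contradict each other outright. They share length of follow-up, and secondary surgery can be read as a safety outcome under section 2.1. The conflict is partial: section 5.2 leaves out operative details and adverse events and speaks of effectiveness.
- A reader might infer that section 5.1 imposes an impossible t-test against baseline on length of follow-up. That sentence covers measurements taken at follow-up time points, which total duration is not. The accurate statement is that no method is given.
- A reader might infer that the endpoints in section 5.2 cannot be analysed at all, or that the t-test is fully specified for VAS and ODI. Both section 5.2 endpoints can be summarised descriptively, and the word Versus in the study title makes a between-group reading of Fisher's test plausible. The t-test, for its part, lacks pairing, sidedness and visit.

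**Conclusion.** The point stands in limited form. Two outcome families, patient-reported outcomes and adverse events or complications, are firmly assigned to different levels in different sections. The placement of operative data and repeat surgery in the section 4.1 list is supporting evidence only. Of the two endpoints in section 5.2, one has no stated method and the other has at most a named test without comparator, time point or allowance for variable follow-up.

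Confidence in the two contradictions is high, because they need no inference beyond treating complications as the adverse-event data. The rejection rates show how a crude comparison could mislead. They rest on assumed hazards, group sizes and follow-up lengths and do not predict this study's result. A reader might also infer an inflated overall error rate from the unqualified 0.05 threshold. The number of tests is not stated, so no such figure forms part of this conclusion.

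**What to change.** Use one primary designation in the Summary and sections 2.1, 4.1, 5.2 and 5.3. The incidence of secondary surgical interventions, already named in section 5.2, is one candidate and would then need naming in section 2.1. Reword the opening sentence of section 4.1 so that patient-reported outcomes fall under the secondary objectives. Place adverse events and complications at one level throughout.

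Report length of follow-up descriptively. For secondary surgery, replace Fisher's test with a time-to-event analysis from index surgery, censored at last recorded follow-up, in one of two forms:

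- cumulative incidence with a 95% confidence interval at a stated time for the coflex group, with no significance claim; or
- a between-group comparison with a named reference group (decompression alone, fusion, or the two pooled), adjusted for collected baseline covariates because the groups are not randomised.

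Censoring deals with unequal length of follow-up, but it assumes that the end of a patient's record is unrelated to reoperation risk. The plan should say so. If two endpoints stay primary and both are tested, split alpha or test in a fixed order.

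The cost is wording, a choice of reference group, time point and covariates, and somewhat more analysis work. Section 4.4.2 already captures the dates of index and repeat surgery. Section 4.4.4 lists no visit date, so confirm that the CRF records the last follow-up date. The downside for the sponsor is that fewer results can be presented as primary.
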